6.1.6. Recruitment and enrolment

Part A of the study includes healthy volunteers and employees from Coloplast A/S. Previously, investigations have been conducted where the participants were employees (e.g. journal No 2004-1-47G) and among especially development engineers, there is a wish to participate in the product development/adhesive development as they can obtain valuable knowledge on how it feels to apply, wear and remove adhesives and thereby use this knowledge for the development of the optimal adhesive for ostomy users. Furthermore, this investigation includes only objective endpoint measurements and therefore, it is considered acceptable to include employees. Employees are seen as a vulnerable group and therefore, recruitment and the informed consent procedure are focusing on voluntariness. The informed consent must be sought by an appropriately qualified individual who is completely independent of this relationship. The Clinical Manager will perform recruitment through advertisement and posters on the Coloplast location at [name] and on Forsoegsperson.dk

The recruitment of potential subjects will commence only once authorisation has been received from Ethics Committee.

If a potential subject is interested in participating, then written information about the investigation (subject information) will be sent to the subject to ensure that potential subjects are given the opportunity to read about the investigation before a possible informational visit, and so that they can prepare any possible questions they may have. The subject information provides information to potential subjects about how to contact the investigator or a representative thereof, or a representative of the sponsor (name, telephone number and e-mail address), if they wish to learn more about the study.

If the potential subject is interested in participating in the investigation, a visit will be arranged in a room reserved for the purpose of ensuring privacy and quiet surroundings at Coloplast. The subjects will receive both written and verbal information about the possibility of bringing a companion to the informational visit and to any possible subsequent visits. See section 13 for information to be given to the subjects, as well as the informed consent process.

6.1.7. Subject withdrawal criteria

The subject is allowed to withdraw from the investigation at any time for whatever reason without any consequences for their employment at Coloplast (part A) or their future treatment outside the clinical investigation (part B). The investigator may withdraw a subject from the investigation at any time if they judge withdrawal to be in the subject's interest.

The investigator must withdraw a subject from the investigation for the following reasons:

- · Non-compliance with the CIP affecting the scientific integrity of the investigation.
- If a subject's safety and well-being is compromised by further participation.
- If it becomes apparent or circumstances change so, a subject do not comply with one or more of the selection criteria.

A subject who is withdrawn from the investigation, for any reason, will be encouraged to contact the investigator if problems arise that the subject believes are related to the clinical investigation. Subjects who have not experienced any adverse events will not be followed up. For subjects who experience adverse events, see section 14.

6.1.8. Point of enrolment

A subject is considered enrolled in the investigation when written informed consent is obtained and the subject has been randomised to a 'treatment' sequence. The expected duration of involvement for each subject is described in section 6.2.1.

6.1.9. Total expected duration of the clinical investigation

The dates below are approximate and no subjects will be enrolled before all required approvals have been obtained. The relevant EC will be notified of changes. The investigation is terminated when the last subject has ended his/her participation.

- First subject enrolled (May/2016).
- Last subject completed (June 2021).

6.1.10. Total number of subjects

Up to 130 subjects will be enrolled in total; up to 80 healthy volunteers will be enrolled in part A and up to 50 subjects with a stoma will be enrolled in part B.

For further information on the number of subjects to be enrolled please refer to the sample size calculation in section 7.2. If the expected number of subjects is not reached within the timelines, the recruitment can be prolonged.

6.2. Procedures

6.2.1. Clinical investigation-related procedures

Before initiation of the clinical investigation, the sponsor must be provided with key investigational personnel's current signed and dated CVs to verify their qualifications. Key site personnel are those who treat or evaluate subject data in the clinical investigation. Also, the sponsor will ensure that all site personnel are trained in the investigation procedures, how to complete the CRFs, the procedure for reporting an adverse event or serious adverse event (how, when, to whom), and who to contact in the case of an emergency related to the investigational device.

Inclusion visit:

- Introduction to the study
- Inclusion in study
- Baseline information is obtained
- Instruct subject to pre-strip of abdominal skin

Test visits 1-25 (up to maximum 25 visits per subject. (1-3 days after pre-stripping the abdominal skin):

- Baseline measurements are conducted on both sides of the stomach (TEWL, hydration, erythema, pH 3 repeated measurements under each adhesive strip area (upper, middle and bottom of adhesive strip)
- Potential wetting of skin shower/bicycle exercise (max 60 minutes) and after-wetting baseline measurements are conducted (TEWL, hydration, erythema, pH 3 times/strips (upper, middle and bottom of adhesive strip))
- Adhesive strips are weighted and applied
- Potential shower/bicycle exercise (max 60 minutes)
- Adhesive strips are removed at pre-defined timeslots (peel force measured)
- Discomfort when strip was peeled of is evaluated by subject (VAS) and discomfort during use of strips are evaluated by questions.
- Measurements are conducted (TEWL, hydration, erythema, pH 3 times/strips (upper, middle and bottom of adhesive strip))
- Acclimatization ½
- Measurements are conducted (TEWL, hydration, erythema, pH 3 times/strips (upper, middle and bottom of adhesive strip))
- Adhesive strips are weighed
- Photo of adhesive strips

For part A: The subjects can be asked to apply and change strips every 24 hours between two test visits but for a maximum of 10 days between two visits. The strips should be applied at the same place every time

For part B: The subjects can be asked to apply and change strips in the abdominal area every 24 hours between two test visits but for a maximum of 10 days between two visits. The strips should be applied at the same place every time

Compliance visit:

A compliance visit is conducted after each cohort has been performed. (minimum. 3 days after last visit).(this can be done by a phone call).

Termination visit:

A termination visit is conducted when subject terminates the study. (minimum. 3 days after last visit).

If the subject experiences skin complications during the visits the investigator or investigator representatives will evaluate the skin condition in order to decide whether subject can continue the study.

For part B, CE-marked ostomy bags are applied to the ostomy to collect output during the test.

6.2.2. Activities performed by sponsor representatives

The investigation will be conducted at a clinical facility at Coloplast, [name]. The Principal Investigator is overall responsible for the investigation. The sponsor representatives will be present at all study activities and all subjects visits.

During the investigation, sponsor's representatives will monitor the investigation closely.

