6.2.4. Flow chart

Table 1 Chart showing scheduled visits and corresponding assessments.

	PERFORMED BY	INFORMATION MEETING	VISIT 1-25	COMPLI- ANCE/TERMINA- TION VISIT
General (performed by investigator)				
Oral information	Independent nurse (part A) Investigator (part B)	x		
Written informed consent	Independent nurse (part A) Investigator (part B)	X		
Randomisation	Investigator		х	
Check of inclusion and exclusion criteria	Investigator	x	X	
Registration of baseline in- formation	Investigator	×		
Registration/measurement of end points				
Stripping abdominal skin*	Subject (1-3 days before each visit)		x	
Apply adhesive strips*	Investigator		х	
Evaluate discomfort (VAS) and discomfort during use of strips evaluated by questions	Subject		×	
Measure peel force, TEWL, hy- dration, erythema and pH	Investigator		x	
Photo of adhesive strips	Investigator		x	
Registration of termination	l)			
AEs/ADEs/SAEs/SADEs	Investigator		×	X
Compliance form	Investigator			Х
Termination form	Investigator			Х

^{*}The subjects themselves can be asked to apply and change the strips every 24 hours between visits (for part B only in the abdominal area). In the case hereof the pre-stripping 1-3 days before a visit will not be applicable.

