12.4. Indemnity

In case of damage as a result of this test the subject are not covered by the general patient compensation system, but covered by the common policies by Danish law concerning compensation. Additionally healthy trial participants are also covered by workers' compensation law. If the participation in the trial is the cause of personal injury, the participant will also be covered by Coloplast's product liability insurance.

13. Informed consent process

Written informed consent is obtained from all subjects participating in the investigation following detailed written and verbal briefing. An independent study nurse in part A of the study (not employed at Coloplast) and the investigator, or his/her representative in part B of the study, provides a non-technical version of this information to the subject in their native language. Each subject will be fully informed about the aim of the investigation, procedures, potential risks or inconveniences and/or expected benefits. Subjects will have time to ask questions and have a minimum of 24 hours before deciding on whether or not to participate in the investigation. Subjects will be informed that their participation is voluntary and that they may leave the investigation at any time, without influencing their further treatment.

The informed consent signature form includes the signatures of the subject and the independent nurse/PI, or his/her representative who is responsible for conducting the informed consent process, which are dated in person. A copy will be provided to the subject.

If new information becomes available during the investigation, the sponsor will inform the investigator, and the new information will be provided to the subjects by the investigator. If new information becomes available that can significantly affect a subject's future health and medical care, the information will be provided to the subjects in written form. The CM is responsible for producing the written information and providing it to investigator who will provide it to the subjects. If applicable, all affected subjects will be asked to confirm their continued, informed consent in writing.

This procedure also applies to informed consent obtained from a subject's legal representative. The procedure does not waive the subjects' legal rights.

For participants, who are not an employee at Coloplast: Confidentiality Agreement between the participant in the study and Coloplast:

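### Section 6.2.2 puts sponsor representatives at every activity and visit without exempting part A consent or employees' discomfort ratings, which works against the plan's voluntariness safeguard and risks response bias in secondary endpoint 8

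*Combined protocol and SAP*

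**What the plan says.** **Attendance.** Section 6.2.2 sets the site and the attendance rule together: "The investigation will be conducted at a clinical facility at Coloplast", and then "The sponsor representatives will be present at all study activities and all subjects visits". Nothing there or elsewhere limits the second sentence.

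**Consent in part A.** Part A recruits both outside volunteers and the sponsor's own employees. Section 6.1.6 gives the reason for special care: "Employees are seen as a vulnerable group and therefore, recruitment and the informed consent procedure are focusing on voluntariness". It then sets the rule: "The informed consent must be sought by an appropriately qualified individual who is completely independent of this relationship". Section 4.2 says the same. Section 13 names the person who informs the subject: "An independent study nurse in part A of the study (not employed at Coloplast"). Table 1 in Section 6.2.4 agrees for both oral information and written consent: "Independent nurse (part A) Investigator (part B"). On the setting, Section 6.1.6 says that "a visit will be arranged in a room reserved for the purpose of ensuring privacy and quiet surroundings at Coloplast", and mentions the option of "bringing a companion to the informational visit and to any possible subsequent visits".

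**Subject ratings.** Secondary endpoint 8 (Section 6.1.2) is discomfort: a VAS at removal and five questions about symptoms during wear. Section 6.2.1 and Table 1 place both at the test visits. Section 6.1.3 describes the VAS as a subjective evaluation, and Section 6.2.6 states that there is no blinding. Even so, Sections 4.2 and 6.1.6 justify enrolling employees on the ground that all endpoint measurements are objective.

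**The concern.** The plan treats employees as open to pressure from their employer and answers this by putting consent in the hands of someone outside the employment relationship. If the employer's representatives also attend that meeting, much of the benefit may be lost, because an employee who is hesitating has to do so in front of the employer.

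The second issue is measurement. At the test visits employees score how unpleasant their own employer's development adhesives are, knowing that the test is open, with the employer's representatives in attendance. Courtesy or caution could push the scores down. The affected data are endpoint 8 and possibly adverse events that come to light only if the subject reports them. Section 6.2.3 nevertheless states that nothing foreseeable is known that could compromise the results.

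**Working it through.** The plan gives no figure to reproduce on this point. The check is a comparison of sections, followed by a bound on reach.

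1. **Does the attendance rule reach the part A consent meeting?** Section 6.2.2 covers all activities and all visits. Section 6.1.6 itself calls the consent meeting an informational visit ("bringing a companion to the informational visit and to any possible subsequent visits"), and it takes place on sponsor premises. Two things point the other way. Table 1 has a column for the information meeting separate from visits 1 to 25. Section 6.1.8 counts a person as enrolled only after consent and randomisation, so those at the meeting are not yet enrolled. The reference to visits is therefore open to argument, but the reference to study activities does not depend on enrolment. Literally read, the meeting is covered, and no section exempts it.

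2. **Is the consent rule broken?** The rule ("The informed consent must be sought by an appropriately qualified individual who is completely independent of this relationship") settles who seeks consent. Table 1 and Section 13 assign that to a nurse from outside the sponsor. No section says who else may or may not attend. The wording of the rule is met; its purpose is not secured.

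3. **Does the attendance rule reach the ratings?** Yes, without ambiguity. Section 6.2.1 and Table 1 put the VAS and the symptom questions inside test visits 1 to 25, and Section 6.2.2 covers all of these.

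4. **Which endpoints could move?**
   - Endpoint 1 (swelling) is a weight difference, so it is not a subject rating.
   - Endpoints 2 to 7 (peel force, adherent area, TEWL, hydration, redness, skin pH) are measured or read by staff or instruments.
   - Endpoint 8 (discomfort) is rated by the subject and is exposed.
   - Endpoint 9 (adverse events) is exposed only so far as events depend on self-report.

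5. **How far does it reach?** Inputs: up to 80 part A subjects (Section 6.1.10) and up to 25 test visits per subject (Section 6.2.1). The ceiling is 80 × 25 = 2,000 subject-visits. With an employee share *p*, at most 2,000 × *p* are employee visits. The plan does not state *p*; it lies between 0 and 1.

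6. **How would a bias show?** Let *d* be the average amount by which employees under-score, and *p_c* the employee share in one cohort. The cohort mean moves by *p_c* × *d*. In the smallest permitted cohort of four (Section 7.2), one employee gives *p_c* = 1/4, so the mean moves by *d*/4; four employees give *p_c* = 1, and it moves by *d*. Neither *p_c* nor *d* is given. If an employee under-scored every strip equally, the shift would cancel in a comparison of strips within that person. It would not cancel in cohort summaries, on which Section 7.1 mainly relies. Nor would it cancel if the under-scoring differed between adhesives, which an open-label design cannot rule out.

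7. **Does the stated reason for enrolling employees cover this?** No. Sections 4.2 and 6.1.6 rest on all endpoints being objective, while Sections 6.1.2 and 6.1.3 include a VAS that the plan itself describes as subjective. These statements are directly inconsistent.

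**The case against.** The best case for the plan is substantial. The person who seeks consent is independent, as required. Section 6.1.6 offers a private room and a companion, and Section 13 allows at least 24 hours to decide. Section 6.1.7 promises that withdrawal has no effect on employment. The subject fills in the VAS on a separate paper sheet (Section 6.2.7). Part A also includes people who are not employees, skin effects are measured by instrument as well, and the investigation is exploratory with no success criterion (Section 7.4).

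Most of this stands, and it limits the point. A reader might infer that Section 6.2.2 flatly contradicts the consent rule or cancels the safeguard. The documents do not support that, because the rule concerns who asks and the independent nurse does the asking. A reader might also picture representatives standing over the subject. The text says only that they are present at the visit; being in the room or watching the form is an inference. Nor do the documents contain evidence that employees under-report.

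What these safeguards do not do is decide who attends the consent meeting, or say that the ratings are completed unobserved. A separate sheet is described only for the VAS, not for the five symptom questions, and staff then measure the VAS mark and enter it. The promise about employment does not deal with who is present when the employee decides or scores.

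**Conclusion.** The point holds as an unreconciled tension with an avoidable risk of bias. The unqualified attendance rule certainly covers the visits at which employees give open-label subjective ratings. On its literal reading it also covers the part A consent meeting, where it works against the voluntariness and privacy that the plan sets out to protect.

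The reach is every employee among up to 80 part A subjects, at consent and at no more than 25 test visits each. The size of any response bias is unknown. The exposure is confined to endpoint 8 for employees and, possibly, self-reported adverse events; the primary weight endpoint is unaffected. For part B this is not an employee issue.

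The conclusion rests on reading Section 6.2.2 as written. If the sponsor never meant its representatives to attend consent, the amendment simply records that. The inconsistency between the claim of objective endpoints and the subjective VAS does not depend on this reading.

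**What to change.** - Amend Section 6.2.2 so that sponsor representatives are not present at the part A information and consent meeting.
- State in Sections 6.2.1 and 6.2.7 that part A subjects mark the VAS sheet, and answer the five symptom questions on a similar self-completed sheet, without sponsor representatives observing.
- Correct the statement in Sections 4.2 and 6.1.6 that all endpoint measurements are objective, and give a justification for enrolling employees that acknowledges endpoint 8.

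The cost is a few sentences, one added paper form for the symptom questions, and its data entry. Consent needs no extra staff, because the independent nurse already takes it.

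The change has limits. It does not address adverse-event reporting or reluctance to withdraw. It also does not keep completed ratings from the sponsor, whose representatives have access to all CRFs (Section 6.3.1), although documents other than the confidential identity file use subject numbers (Section 12.3).

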6.2.3. Foreseeable factors that may compromise the outcome/results

There are no known foreseeable factors that may compromise the outcome of this investigation.

6.2.4. Flow chart

Table 1 Chart showing scheduled visits and corresponding assessments.

	PERFORMED BY	INFORMATION MEETING	VISIT 1-25	COMPLI- ANCE/TERMINA- TION VISIT
General (performed by investigator)				
Oral information	Independent nurse (part A) Investigator (part B)	x		
Written informed consent	Independent nurse (part A) Investigator (part B)	X		
Randomisation	Investigator		х	
Check of inclusion and exclusion criteria	Investigator	x	X	
Registration of baseline in- formation	Investigator	×		
Registration/measurement of end points				
Stripping abdominal skin*	Subject (1-3 days before each visit)		x	
Apply adhesive strips*	Investigator		х	
Evaluate discomfort (VAS) and discomfort during use of strips evaluated by questions	Subject		×	
Measure peel force, TEWL, hy- dration, erythema and pH	Investigator		x	
Photo of adhesive strips	Investigator		x	
Registration of termination	l)			
AEs/ADEs/SAEs/SADEs	Investigator		×	X
Compliance form	Investigator			Х
Termination form	Investigator			Х

^{*}The subjects themselves can be asked to apply and change the strips every 24 hours between visits (for part B only in the abdominal area). In the case hereof the pre-stripping 1-3 days before a visit will not be applicable.

6.2.5. Randomisation procedure

If applicable, randomisation will be performed within each cohort. The investigator/investigator representative will receive sealed envelopes containing consecutive numbers, which indicate the subjects randomisation numbers and test set-up. The randomisation lists are generated using SAS version 9.4 or JMP® version 12. The Randomisation lists are archived in the Sponsor File.

6.2.6. Blinding

This investigation is not blinded.

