6.1. General

The investigation is open-labelled and is divided into two parts: Part A evaluates the adhesive strips on abdominal skin in healthy volunteers while part B evaluates the adhesive strips on peristomal and abdominal skin in people with a stoma.

Part A:

Investigation of adhesive strips will be performed in cohorts of minimum 4 and up to 80 subjects. Each cohort consist of 1 or more test visits and a compliance visit. The purpose of the investigation for the individual cohorts will be described in a sub-investigation document.

At each of the test visits, subjects have a maximum of six adhesive strips placed on the skin as illustrated in Figure 1. The adhesive strips are placed on either dry skin or skin wetted by buffer or simulated output. The adhesive strips can be removed at different time slots but after 72 hours at the latest (e.g. after 10, 60 minutes and 24 hours) or within the same time slot.

The ordering of the timeslots position (T1, T2 and T3) from belly - button will be randomized within each cohort if applicable.

Subjects can be asked to take a shower or ride an exercise bicycle for max 1 hour before application of adhesive strips or during wear.

Subjects can also be asked to apply and change adhesive strips every 24 hours between visits but for a maximum of 10 days between two visits. The strips should be applied at the same place every time

Each adhesive strip will be evaluated in a cohort of minimum 4 subjects and up to 80 subjects are enrolled and can test maximum 30 different types of adhesive strips.

Example illustrating test of adhesive strips. T1, T2 and T3 indicates different time slots for removing adhesive strips e.g. 10, 60 minutes and 24 hours:

[figure not shown]

Figure 1

Part B:

At each of the test visits, subjects have a maximum of four adhesive strips placed on the skin as illustrated in the Figure 2. The adhesive strips are placed on either dry skin or skin wetted by buffer, real or simulated output. The adhesive strips will be removed at different time slots but after 72 hours at the latest.

Subjects can be asked to take a shower or ride an exercise bicycle for max 1 hour before application of adhesive strips or during wear.

Subjects can also be asked to apply and change adhesive strips in the abdominal area every 24 hours between visits but for a maximum of 10 days between two visits. The strips should be applied at the same place every time.

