6.1.2. Secondary end points

Secondary endpoints:

- 2. Peel force needed to peel off adhesive strip (assessed when possible)
- 3. Adherent area on adhesive strip assessed by photos and measured by area (cm²) or ordinal point scale ranging from very small to very large.
- 4. Trans Epidermal Water Loss (TEWL)
- 5. Hydration measured by conductance
- 6. Redness of skin (erythema) assessed by spectrophotometric method, thermography, photos and potential video sequences
- 7. pH of skin
- 8. Discomfort when adhesive strip is peeled off evaluated by the Visual Analogue Scale (VAS) and discomfort during use of adhesive strips evaluated by following questions: 1) Have you experienced any redness under the adhesive? 2) Have you experienced any itching or burning under the adhesive? 3) Do you experience any weeping or moisture on the skin under the adhesive? 4) Have you experienced any pain under the adhesive? 5) Do you experience any bleeding from the skin under the adhesive? The severity of redness, itching and burning, weeping and moisture, pain and bleeding will be rated as None of the time, A little of the time, Some of the time, A lot of the time or All of the time.
- 9. Adverse events

TEWL, hydration, occurrence of erythema and pH of the skin are measured by three repeated measurements.

Baseline data:

Age Gender Height/weight Informed Consent

For Part B the following will be included as well:

Year of stoma

Type of stoma

Reason for stoma

Leakage pattern

Experiences with moisture and product performance (e.g. skin maceration, leaks after physical activities etc.)

– Answer is a comment field

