Discomfort: The VAS is an instrument used to subjectively evaluate the discomfort when the strip is peeled off. The subject will be asked to mark the evaluation as a vertical line on the 10 cm horizontal VAS ranging from "no discomfort" to "worst possible discomfort" caused when the strip is peeled off. Discomfort during use

of adhesive strips evaluated by questions regarding subject experience in redness under the adhesive, feeling of itching and burning under the adhesive, weeping or moisture under the adhesive, pain and bleeding from the skin.

User experience is a very important part of product development in Coloplast A/S and the selected questions relate to how the adhesive strips affects the skin.

Adverse Events: All adverse Events are captured and documented throughout the study.

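### The study is unblinded without a stated reason, and the plan does not say whether strips are coded, although subjects (in part A possibly adhesive developers) rate discomfort themselves

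*Combined protocol and SAP*

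**What the plan says.** - **Blinding.** Section 6.1: "The investigation is open-labelled and is divided into two parts". Section 6.2.6: "This investigation is not blinded". Neither gives a reason or says that masking was considered.
- **Strips.** Section 2 says only that they differ in water absorption. Appearance, thickness, labelling and coding are not described.
- **Subjects.** Section 6.1.6: "Part A of the study includes healthy volunteers and employees from Coloplast A/S". It adds that "among especially development engineers, there is a wish to participate in the product development/adhesive development". The number or share of employees or engineers is not given.
- **Grounds for admitting employees.** Section 6.1.6: "this investigation includes only objective endpoint measurements and therefore, it is considered acceptable to include employees". Section 4.2 makes the same argument.
- **Subject-rated endpoints.** Secondary endpoint 8 in section 6.1.2 has two parts: a VAS at peel and five questions on discomfort during use, each with five frequency levels. Section 6.1.3: "The VAS is an instrument used to subjectively evaluate the discomfort when the strip is peeled off". Table 1 assigns both ratings to the subject. Adverse events are endpoint 9 and are registered by the investigator.
- **Setting.** Up to six strips (part A) or four (part B) are worn at a visit (section 6.1). Section 6.2.2: "The sponsor representatives will be present at all study activities and all subjects visits".
- **Use of results.** Sections 7.1 and 7.5 have data analysed cohort by cohort to guide which adhesives are developed and tested next.

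**The concern.** A subject who wears several adhesives at once compares them directly. If that subject knows which is which and has a view on which should do well, the view can enter the VAS mark, the five answers and the choice of which symptoms to mention. In part A some subjects may have developed the adhesives. Staff who peel, place probes and measure the VAS line (section 6.2.7) may also know the adhesive.

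The plan's stated safeguard for employees is that every endpoint is objective. That cannot hold for an endpoint the plan itself calls subjective. At stake are the between-adhesive comparisons on discomfort and reported symptoms, which feed the next round of development. Adding subjects makes such a bias look more certain without making it smaller.

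**Working it through.** **1. The passages side by side.** Sections 4.2 and 6.1.6 rest the enrolment of employees on the absence of subjective endpoints. Sections 6.1.2 and 6.1.3 and Table 1 contain six subject-rated items: one VAS and five questions. This contradiction stands without any assumption about labels or appearance.

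**2. Whether masking is covered elsewhere.** Section 6.2.5 provides sealed envelopes, where randomisation applies, showing the randomisation number and test set-up. They conceal allocation before use and do not mask the strip. Section 12.3 speaks of blinded data, but this concerns the subject's identity. Nothing in the plan addresses strip identity.

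**3. Size.** The plan gives no SD, no bias estimate and no effect size, so there is no figure to reproduce. The following is an illustration.

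Inputs:
- Two adhesives truly equal on the VAS, compared within subjects.
- Expectation shifts the mean paired difference by d SDs of that difference. This is assumed, with range 0.2 to 0.5.
- Two-sided 5% test. Section 7.3 gives the 5% level for exploratory analyses; two-sidedness is assumed.
- Cohort sizes n = 4 (the minimum), 20 and 50. Section 6.1 allows up to 80 in part A.

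Formula: with df = n − 1 and noncentrality λ = d√n, the false-positive probability is P(|T| > c). T is noncentral t with df and λ, and c is the 97.5% point of central t.

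| n | c | d = 0.2: λ | probability | d = 0.3: λ | probability | d = 0.5: λ | probability |
|---|---|---|---|---|---|---|---|
| 4 | 3.182 | 0.40 | 6% | 0.60 | 7% | 1.00 | 11% |
| 20 | 2.093 | 0.89 | 14% | 1.34 | 25% | 2.24 | 56% |
| 50 | 2.010 | 1.41 | 28% | 2.12 | 55% | 3.54 | 93% |

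λ is also the bias in units of the standard error. It therefore shows how far a summary mean is displaced relative to its precision when no test is run. At n = 4 the displacement is 0.4 to 1.0 standard errors; at n = 20 it is 0.9 to 2.2.

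**4. What d requires.** d is a shift in the cohort mean, so subjects must on average lean the same way. If one subject in five were an engineer (assumed) and the rest neutral, each engineer would have to shift by 0.2/0.2 = 1.0 SD to reach d = 0.2, and by 0.5/0.2 = 2.5 SD to reach d = 0.5. The upper end therefore needs either many subjects with a shared expectation or very strong individual ones.

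**The case against.** The strongest reply is that this is an exploratory pilot with no pass/fail criteria (section 7.4). Its primary endpoint is a weight difference, its evaluation rests mainly on summary statistics (sections 7.1 and 7.3), and laboratory data also inform development. Discomfort is one of eight secondary endpoints and is not named in any objective in section 5.1. At the minimum cohort of four, even the largest assumed shift raises the false-positive rate only from 5% to 11%. All of this stands and limits the weight of the point. It does not remove the point, because discomfort is collected to compare adhesives and cohorts may be much larger than four.

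Some stronger readings are tempting but not supported:

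- *A reader might infer that strips are uncoded and that subjects know what they wear.* An open-label study can still use coded strips, and the plan is silent on both points.
- *A reader might infer that a label would hide identity.* Appearance and thickness are not described, and a developer might recognise a formulation despite a code.
- *A reader might infer that the existing randomisation list already supplies a key.* Randomisation is conditional (section 6.2.5). Section 6.1 describes randomising only the order of time-slot positions and does not mention adhesives.
- *A reader might extend the engineer argument to the whole study.* It applies to part A; part B enrols people with a stoma.
- *A reader might infer that the device-relatedness judgement is biased too.* Section 14.1.2 asks whether an event is related to the device, which does not require knowing the formulation. The exposure lies in which symptoms subjects report.
- *A reader might conclude that developers should be barred from cohorts testing their own adhesive.* That would reverse a deliberate recruitment choice explained in sections 4.2 and 6.1.6. It is a debatable trade-off and is not requested here.

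**Conclusion.** The point holds in limited form. The plan is open-label without a reason, is silent on coding and on what subjects are told, and admits employees on a ground that its own endpoint list contradicts. Expectation can bias between-adhesive comparisons on endpoint 8 and on subject-reported events. The weight-based primary endpoint does not depend on subject report.

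The size cannot be derived from the documents. The illustrative range is about 6–11% false-positive results at n = 4 and 14–56% at n = 20. It rests on an assumed shift of 0.2 to 0.5 SD in a common direction and on a paired test that the plan does not specify. A smaller or mixed-direction effect would give less. The contradiction about objective endpoints needs no such assumption.

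**What to change.** **Section 6.2.6** should state the following:

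- Where adhesives cannot be told apart by sight, strips carry neutral codes, subjects are not told the adhesive, and staff who peel and measure work from the code.
- The sponsor holds the key until the cohort's data are final. The investigator can obtain it at any time for safety. This matters because section 6.2.1 has the investigator or representatives evaluate skin complications.
- Skin condition and time slot remain open.
- Where adhesives look different, the plan says so and the discomfort results are reported as open-label.

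**Sections 4.2 and 6.1.6** should no longer say that all endpoints are objective. They should acknowledge the subject-rated discomfort endpoint and justify enrolling employees with that in view.

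**Cost.** A code list and some labelling work per cohort. Masking will be only partial if adhesives differ in appearance. No endpoint, visit or eligibility rule changes.
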